9.3.4 SF36v2 and PCS Domain Scores

The SF-36 is the most widely used general health-related quality of life instrument in clinical trials, with a rich and diverse body of psychometric supporting data. The SF-36v2 is a multipurpose, 36-item subject-completed validated questionnaire that measures 8 domains of health: physical functioning, role limitations due to physical health, bodily pain, general health perceptions, vitality, social functioning, role limitations due to emotional problems, and mental health. The SF-36v2 survey with a 4-week recall will be used. It yields scale scores for each of these 8 health domains, and two summary measures of physical and mental health, respectively: the PCS and MCS.

The SF-36v2 includes algorithms for interval level scoring for all eight scales ranging from 0 (for worse health) to 100 (best possible health as measured by the questionnaire), as well as the same standardized scoring (mean = 50, standard deviation = 10) for the SF-36 summary scores (PCS and MCS).

The SF-36v2 scoring will be performed according to the current SF-36v2 algorithm and specifications for missing data using proprietary software provided by Optum PRO CoRE. The resulting t-scores will be analyzed as described in Sections [7.5.6](#), [7.5.7](#).

9.3.5 Acute CRS Exacerbations

An acute exacerbation of chronic rhinosinusitis event is defined as a worsening of symptoms requiring antibiotic or corticosteroid use, specifically:

- An acute worsening of one or more of the cardinal diagnostic symptoms of chronic rhinosinusitis (listed below), lasting at least 3 days, that causes the subject to seek medical care:
 - facial pain or pressure
 - nasal congestion/blockage
 - rhinorrhea
 - reduction in sense of smell

AND

- An escalation of treatment, defined as either initiation of treatment with antibiotics or systemic steroids, or the escalation of treatment involving an unscheduled acute care visit (e.g., emergency room or out subject clinic) or in-subject care, for increased symptoms related to sinusitis.

Date of onset of a CRS exacerbation event is defined by on the earliest onset date reported on the Exacerbation CRF; differentiation between CRS exacerbation events will also be determined from the onset dates reported on the Exacerbation CRF. If CRS exacerbation event start date is less than 7 days after the end date of a previous exacerbation, the entire period will be treated as a single exacerbation.

Duration of double blind period for each subject will be derived for this analysis as:

$$\text{Duration (days)} = (\text{Week 24/ET visit date} - \text{Date of Day 1}) + 1.$$

This duration of DB period will be the follow-up (exposure) time for analysis; subjects who did not experience any CRS exacerbation events during the DB period will be assigned '0' for frequency.

The time (weeks) to first acute CRS exacerbation event is defined as:

$$\frac{\text{start date of first CS exacerbation} - \text{date of randomization} + 1}{7}$$

9.3.6 Qualitative CT Scan Image Assessment

The protocol for qualitative CT scan imaging assessments is based on the Image Review Charter (IRC) – Revision C, (29 January 2020). Qualitative CT scan assessments will be performed at baseline and Week 24/ET in accordance with the IRC for Lund-Mackay Staging and Zinreich Modification of the Lund-Mackay Staging.

As described in the IRC, two radiologist reviewers and a third adjudicating radiologist reviewer will independently review and score the CT scan images. When there are discrepant scores between the two primary reviewers, the adjudicating reviewer will review the image and choose a score recorded by one of the primary reviewers.

Specifically, the adjudicated value is assigned as follows, where R3 represents the adjudicating radiologist, and R1, R2 represent the Radiologist reviewers:

- If R1 and R2 agree, then the adjudicated value is the value of R1 and R2.
- If R1 and R2 both have an integer value and they disagree, then R3 reviews the CT scan image and chooses one of those integer values and that is also the adjudicated value.
- If one of R1 or R2 is 'Unable to Assess,' then R3 reviews the CT scan image and records either the integer value of R1 or R2 or 'Unable to Assess.'

Lund-Mackay (LM) Staging

The LM sinus (Lund and Mackay, 1993) score will be graded separately for all 10 sinuses listed in Table 9.5, as well as the ostiomeatal complex, (12 total LM scores). The sinuses are scored: 0 (no abnormality), 1 (partial opacification), or 2 (total opacification), and the ostiomeatal complex is scored: 0 (not obstructed), or 2 (obstructed).

LM Scores for the sinuses will be derived from the Zinreich Modification of the Lund-Mackay Staging System (ZLM) scores, which are defined below.

- ZLM scores of 0 will = 0 on LM
- ZLM scores of 1, 2, 3, or 4 will = 1 on LM
- ZLM scores of 5 will = 2 on LM
- The LM score for the OMC is captured as defined above.

The following variables are defined based on LM scores:

- LM Total Score: sum of 12 LM scores. Therefore, the total LM score for a CT scan ranges from 0-24.
- LM scores for ethmoids and maxillary sinuses combined: The sum of the two ethmoid and one maxillary sinuses listed in Table 9.5, including the left and right sinus for each. The score for the total of six sinuses ranges from 0 to 12.
- LM Score for each Sinus Pair: For each of the 5 sinuses listed in Table 9.5, the left and right sinus pair is summed. Each sinus pair listed in Table 9.5 will be analyzed separately. These variables range from 0 to 4.

Zinreich Modification of the Lund-Mackay Staging (ZLM)

The Zinreich Modification of the Lund-Mackay Staging System ([Zinreich 2004](#)), the ZLM score, is also graded separately for all 10 sinuses listed in Table 9.5. The scoring is as follows.

Score 0: 0% opacification of the sinus

Score 1: 1% to 25% opacification of the sinus

Score 2: 26% to 50% opacification of the sinus

Score 3: 51% to 75% opacification of the sinus

Score 4: 76% to 99% opacification of the sinus

Score 5: 100% opacification of the sinus

The following variables are defined based on ZLM scores:

- ZLM Total Score: sum of 10 ZLM scores. Therefore, the total ZLM score for a CT scan ranges from 0-50.
- ZLM scores for ethmoids and maxillary sinuses combined: The sum of the two ethmoid and one maxillary sinuses listed in Table 9.5, including the left and right sinus for each. The score for the total of six sinuses ranges from 0 to 30.
- ZLM Score for each Sinus Pair: For each of the 5 sinuses listed in Table 9.5, the left and right sinus pair is summed. Each sinus pair listed in Table 9.5 will be analyzed separately. These variables range from 0 to 10.
- WZLM score is the score for the worst sinus among the anterior ethmoid (L, R), posterior ethmoid (L, R), and maxillary (L, R) sinuses (all 6 sinuses) at baseline. In the event of a tie, the rule is: use the right sinus, then use the ethmoid sinus, then use the anterior ethmoid sinus. The change in this sinus at Week 24/ET is the endpoint of interest.

Table 9.5: Sinuses (Left and Right) Assessed and Scored

Sinus (Left, Right)	LM Score	ZLM Score
Ethmoid Anterior	✓	✓
Ethmoid Posterior	✓	✓
Frontal	✓	✓
Maxillary	✓	✓
Sphenoid	✓	✓
Ostiomeatal Complex	✓	

Missing Qualitative CT Scan Image Measurements

Qualitative LM and ZLM measurements of a sinus may be missing due to technical issues that are unrelated to disease measurement; these measurements are reported as ‘Unable to Assess’ through the adjudication process.

Rules for handling missing qualitative ZLM scores in an individual sinus are as follows: If the qualitative CT scan measurements in any sinus are missing at baseline, then the subject will be excluded from the FAS population. If the qualitative CT scan measurement in any sinus are missing at Week 24/ET, then the measurement for that sinus will be replaced by the corresponding baseline measurement. As described above, LM scores are derived from ZLM scores, except for the LM Ostiomeatal Complex which will use this missing data rule as well.

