#### **9.2.3 Full Analysis Set (FAS)**

The FAS will include all subjects in the ITT set who receive at least one dose of randomized study drug during the double-blinded treatment phase and have at least one baseline efficacy measure for APOV endpoint, and also have a baseline value and at least one post-baseline value (7-day average AM instantaneous CSNS score) on or before Week 4 (i.e., Week 2 and/or Week 4) for the CSNS endpoint. Subjects will be included in the treatment group to which they were randomized.

The FAS population will be the primary study population for all efficacy analyses in this study.

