5.5 Full Analysis Set (FAS)

The FAS will include all subjects in the ITT set who receive at least one dose of randomized study treatment during the double-blinded treatment phase and have a baseline efficacy measurement for APOV endpoint, and also have a baseline value and at least one post-baseline value (7-day average AM instantaneous CSNS score) on or before Week 4 (i.e., Week 2 and/or Week 4) for the CSNS endpoint. Subjects will be included in the treatment group to which they were randomized.

The FAS population will be the primary study population for all efficacy analyses in this study.

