9.3.2 Quantitative (Volumetric) Measurement of CT Scan Image

The protocol for quantitative (volumetric) measurement of CT scan imaging is based on the Image Review Charter (IRC) – Revision C, (29 January 2020). Quantitative measurement of Sinus Volume and Opacification Volume will be performed by a trained analyst under the supervision of a Biomedical Engineer using a validated software system as described in the IRC.

The following quantitative variables are defined for each of the four sinuses: Maxillary (Left, Right), Ethmoid (Left, Right).

Sinus Volume (SV): the total volume of the specified sinus cavity regardless of the amount of mucosal inflammation that may be present. Total Sinus Volume will consist of both the soft tissue and air signal within the specified sinus. Sinus Volume will be reported in cubic millimeters.

Opacification Volume (OV): the total volume of the soft tissue and mucosal inflammation as visualized in the specified sinus. Opacification Volume will be reported in cubic millimeters.

Percentage of Opacified Volume (POV): $POV = OV/SV \cdot 100\%$

Missing Volumetric Measurements

Volumetric measurements (SV, OV) of a sinus may be missing due to technical issues that are unrelated to disease measurement; these measurements are reported as 'Unable to Assess.'

If the volumetric measurements in any sinus are missing at baseline, then the subject will be excluded from the FAS population. If either of the volumetric measurements in any sinus is missing at Week 24/ET, then the volumetric measurement for that sinus will be replaced by the baseline volumetric measurement.

Average Percentage of Opacified Volume (APOV)

APOV is the average percentage of opacified volume across both maxillary (L, R) and ethmoid (L, R) sinuses (all 4 sinuses) at each time point (Baseline, Week 24/ET). Larger values of APOV,

i.e., higher percentages of opacified volume, indicate greater severity of CRS; therefore, negative values for change from baseline APOV indicate improvement from baseline.

APOV-E is the average percentage of opacified volume in the ethmoid (L, R) sinuses at each time point (Baseline, Week 24/ET).

APOV-M is the average percentage of opacified volume in the maxillary (L, R) sinuses at each time point (Baseline, Week 24/ET).

Worst Percentage of Opacified Volume (WPOV)

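### SAP 9.3.6 removes a subject from the whole FAS for any unreadable baseline Lund-Mackay or Zinreich score, a condition absent from the FAS definitions and irrelevant to both co-primaries

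*SAP*

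**What the plan says.** Two places define the FAS, and they agree. Beyond randomisation and a double-blind dose, Protocol 9.2.3 requires that subjects "have at least one baseline efficacy measure for APOV endpoint, and also have a baseline value and at least one post-baseline value" for CSNS by Week 4. SAP 5.5 requires that they "have a baseline efficacy measurement for APOV endpoint, and also have a baseline value and at least one post-baseline value", with the same time limit. Neither mentions LM or ZLM scores. SAP 5.5 adds: "The FAS population will be the primary study population for all efficacy analyses in this study".

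SAP 9.3.6, under missing qualitative CT measurements, adds a further exclusion: "If the qualitative CT scan measurements in any sinus are missing at baseline, then the subject will be excluded from the FAS population". The next sentence handles a missing Week 24/ET score by carrying in the baseline score. LM sinus scores are derived from ZLM scores, "except for the LM Ostiomeatal Complex which will use this missing data rule as well".

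A missing score here means one still recorded as unable to assess after adjudication. The same section gives the cause: "Qualitative LM and ZLM measurements of a sinus may be missing due to technical issues that are unrelated to disease measurement".

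SAP 9.3.2 has a parallel rule for the volumetric data: "If the volumetric measurements in any sinus are missing at baseline, then the subject will be excluded from the FAS population".

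**The concern.** The sentence in 9.3.6 acts on the FAS itself, not on the LM and ZLM analyses. Take a randomised, dosed subject with complete diaries, usable volumetry in all four APOV sinuses, and one frontal sinus that could not be graded at baseline. Under SAP 5.5 this subject is in the FAS. Under SAP 9.3.6 the subject is out, and so leaves both co-primary analyses and every other efficacy analysis run on the FAS.

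Two things are at stake. The primary population is ambiguous, because the answer depends on which section the programmer follows. And if 9.3.6 is followed, usable randomised subjects are discarded for a cause the SAP itself treats as technical, with some loss of precision. Bias between arms is not the issue, because the baseline scan is read before treatment starts.

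**Working it through.** **1. Does either co-primary use the qualitative scores?**

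- CSNS (SAP 9.3.1) is the sum of three diary symptom scores. It has no CT input.
- APOV (SAP 9.3.2) is built from opacified volume divided by sinus volume: "APOV is the average percentage of opacified volume across both maxillary (L, R) and ethmoid (L, R) sinuses (all 4 sinuses". It has no LM or ZLM input.
- LM and ZLM scores feed other secondary endpoints with nominal p-values (SAP 7.5.4), and an LM score is one of the surgical-eligibility criteria (SAP 7.6.1).

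**2. How many readings can trigger the exclusion?**

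SAP 9.3.6 and Table 9.5 list five sinuses on each side, giving 10 ZLM scores, plus the left and right ostiomeatal complex (OMC). That is 12 readings.

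- Six (frontal, sphenoid and OMC, left and right) grade structures that do not enter APOV.
- Six (maxillary, anterior ethmoid and posterior ethmoid, left and right) grade sinuses for which 9.3.2 already decides whether baseline APOV is usable.

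The volumetric rule in 9.3.2 follows from the baseline-APOV condition in the FAS definition. The qualitative rule follows from nothing in that definition.

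**3. The plan's own power figure.**

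Inputs from Protocol 9.1 and SAP 4.2: 111 per arm, two-sided 5%, CSNS difference 0.8 with SD 1.9, APOV difference 11.3 with SD 27, stated power 88% for each.

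Noncentrality = difference / (SD × √(2/n)).

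- CSNS: 0.8 / (1.9 × √(2/111)) = 3.14, noncentral t power 87.8%.
- APOV: 11.3 / (27 × √(2/111)) = 3.12, noncentral t power 87.4%.

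The normal approximation gives 88.0% and 87.7%. The stated 88% is reproduced.

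**4. What the rule could cost.**

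The documents give no rate of unreadable scores, so the rate is an assumption: p = 0.2% to 2% per reading. With k readings able to trigger exclusion independently, the share excluded is 1 − (1 − p)^k and the remaining n per arm is 111 × (1 − p)^k. Taking k = 1 represents full clustering, where a poor scan fails as a whole.

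| Scenario | Excluded | Of 333 | n per arm | CSNS power | APOV power |
|---|---|---|---|---|---|
| k = 1, full clustering | 0.2%–2.0% | about 1–7 | 110.8–108.8 | 87.7%–87.1% | 87.3%–86.7% |
| k = 4, frontal and sphenoid only | 0.8%–7.8% | about 3–26 | 110.1–102.4 | 87.5%–85.0% | 87.1%–84.6% |
| k = 6, frontal, sphenoid and OMC | 1.2%–11.4% | about 4–38 | 109.7–98.3 | 87.4%–83.6% | 87.0%–83.1% |
| k = 12, all readings (upper end) | 2.4%–21.5% | about 8–72 | 108.4–87.1 | 87.0%–78.9% | 86.6%–78.4% |

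For example, k = 6 at p = 2%: 1 − 0.98^6 = 11.4%, and 111 × 0.98^6 = 98.3 per arm.

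**The case against.** The strongest reply is that this is a drafting slip of small effect.

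- **Size.** Several filters lower the rate. A missing score must survive adjudication, in which one reader's integer score can be adopted. The scan is reviewed centrally before randomisation (Protocol 3.1). Routine-care scans must meet the Imaging Charter standard. Exclusion criterion 6 removes anatomy that prevents volume assessment. Technical faults also tend to affect a whole scan, which points to the k = 1 row. This stands as a reason to expect a small loss. It does not remove the problem. Exclusion criterion 6 concerns sinus volume, inclusion criterion 6 needs an LM score of 1 or more in only one sinus per side, and SAP 9.3.6 itself expects unreadable scores.
- **The k = 12 row is gross.** Where the same fault also spoils maxillary or ethmoid volumetry, 9.3.2 already excludes the subject, so deleting the 9.3.6 rule would not bring that subject back. This is right. The row is an upper end, and k = 4 or k = 6 isolates the structures outside APOV.
- **The OMC reading is uncertain.** The clause on the OMC follows the Week 24 replacement sentence and could refer to that alone. The more natural reading covers the baseline rule too, but the k = 4 row shows the result without it.
- **Perhaps only the LM and ZLM endpoints were meant.** That is possible, but the sentence names the FAS population. If the narrower meaning was intended, the wording has to change anyway.
- **The change log.** SAP section 11 does not list this restriction, and SAP section 2 says there are no deviations from the amendment. This is weak support only. Section 11 covers changes made after Amendment 6.0, and the rule may have stood in an SAP we do not have.

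**Conclusion.** The concern holds. As written, SAP 9.3.6 adds an FAS exclusion that contradicts Protocol 9.2.3 and SAP 5.5 and has no bearing on either co-primary. This rests on the text alone and needs no assumption about rates.

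The numerical cost is uncertain and may be negligible: under one point of power if unreadable scores cluster within scans, and about four points for either co-primary at the top of the assumed range if the six readings outside APOV fail independently. Those figures depend on the assumed 0.2% to 2% per reading and on the independence assumption, neither of which the documents support or refute.

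It should be fixed because the primary population has to be unambiguous before unblinding and the correction costs almost nothing.

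**What to change.** Replace the quoted sentence in SAP 9.3.6 with wording such as: *A subject with a missing baseline ZLM score, or a missing baseline LM score for the OMC, is left out only of the LM and ZLM analyses that use that score; FAS membership is unaffected.* Keep the volumetric baseline rule in SAP 9.3.2 as it is, since it defines when baseline APOV is usable.

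Two small checks go with it:

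- State how a missing baseline LM score is handled in the surgical-eligibility assessment (SAP 7.6.1).
- Confirm that the SAP for Study OPN-FLU-CS-3206 uses the same rule, because the key secondary analyses pool the two studies. That document is not available here.

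The cost is one sentence and these checks, with no new data. The change can only add subjects to the FAS. SAP 4.5 describes the plan as final, so it would need a dated SAP amendment before unblinding.

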9.3.7 Pittsburgh Sleep Quality Index (PSQI)

PSQI is a validated, self-rated questionnaire, which assesses sleep quality and disturbances over a 1-month time interval. Nineteen individual items scored 0 (no difficulty) to 3 (severe difficulty) generate 7 component scores: subjective sleep quality, sleep latency, sleep duration, habitual sleep efficiency, sleep disturbances, use of sleeping medication, and daytime dysfunction. The sum of scores for these 7 components yields a global score (range 0 to 21). Higher scores indicate worse sleep quality. Refer to Section 7.5.5 for analysis and Section 13.1, Appendix 1: PSQI Scoring for the scoring algorithm of the PSQI instrument ([Buysse, DJ 1989](#)).

9.3.8 PGIC - “Subject” Global Impression of Change

“Subject” Global Impression of Change (PGIC) is assessed based on a 7-point Likert scale as shown in Table 9.6. Two endpoints are defined based on a dichotomization of the scale. Category 1 (Improved) is defined as any improvement (minimally, much, very much); Category 2 (Much Improved) is defined as improvement (much, very much). Reference Section 7.5.8 for analysis.

Table 9.6: Subject Global Impression of Change (PGIC) Scale

Since starting the study drug, how would you rate the change in your symptoms?			
Score	Description	Category 1	Category 2
1	Very much improved	Improved	Improved
2	Much improved	Improved	Improved
3	Minimally improved	Improved	Not improved
4	No change	Not improved	Not improved
5	Minimally worse	Not Improved	Not Improved
6	Much worse	Not improved	Not improved
7	Very much worse	Not Improved	Not Improved
Missing	Missing	Not Improved	Not Improved

9.3.9 Quick Inventory of Depressive Symptomatology – Self Report (QIDS-SR)

The 16-item QIDS-SR ([Rush et al, 2003](#)) is designed to assess the severity of depressive symptoms. The QIDS-SR is a self-report version and assesses all the criterion symptom domains designated by the American Psychiatric Association Diagnostic and Statistical Manual of Mental Disorders – 5th Edition to diagnose a major depressive episode.

Sixteen individual items are scored 0 to 3 with lower scores indicating lower severity of depression. The 7-day period prior to assessment is the usual time frame for assessing symptom severity. Severity of depression will be assessed based on the total score (range 0-27) and categories of the severity of depression as shown in Table 9.7.

If any item Q1-Q5, Q10-Q16 is missing, or if either of ((Q6 and Q7) or (Q8 and Q9)) are missing, then the total QIDS-SR score is missing. If either of Q6 or Q7 is answered and either of Q8 or Q9 is answered the questionnaire can be categorized by severity of depression as described in Table 9.7.

The QIDS-SR total score is the summation of the following items:

- The highest score from Q1-Q4
- Response from Q5
- The highest score from Q6-Q9
- Responses from Q10, Q11, Q12, Q13, Q14
- The highest score from Q15 and Q16

Table 9.7: QIDS-SR Severity of Depression Categories

QIDS Score	Severity of Depression
0 – 5:	None
6 – 10:	Mild
11 – 15:	Moderate
16 – 20:	Severe
21 – 27:	Very Severe

9.4 Health Economic Outcomes Research (HEOR) Endpoints

9.4.1 EQ-5D-5L

The EQ-5D-5L is a standardized measure of health status developed to provide a simple, generic measure of health for clinical and economic appraisal.

The five-level EQ-5D (EQ-5D-5L) consists of 2 pages: the EQ-5D descriptive system and the EQ visual analogue scale (EQ VAS). The descriptive system comprises 5 dimensions: mobility, self-care, usual activities, pain/discomfort, and anxiety/depression. And each dimension has 5 levels: no problems, slight problems, moderate problems, severe problems, and extreme problems. The subject is asked to indicate his/her health state by ticking the box next to the most appropriate statement in each of the 5 dimensions. This decision results in a 1-digit number that expresses the level selected for that dimension. The digits for the 5 dimensions can be combined into a 5-digit number that describes the subject's health state. EQ-5D-5L dimension is scored using algorithms obtained from the EuroQol Group authors.

Each dimension is coded according to the level selected by the subject as follows: 1=no problems, 2=slight problems, 3=moderate problems, 4=severe problems, 5=extreme problems. Missing dimension values and ambiguous values (2 values selected for the same domain) coded as '9' will be changed to missing in the analysis dataset.

The EQ VAS records the subject's self-rated present health on a vertical visual analogue scale, in response to the statement, "*We would like to know how good or bad is your health TODAY.*" The endpoints on the VAS are labelled 100: 'The best health you can imagine' and 0: 'The worst health you can imagine'. The VAS can be used as a quantitative measure of health outcome that reflect the subject's own judgement. The VAS is scored as collected and should have a number between

0-100. Missing values coded as '999' for this instrument will be changed to missing in the analysis dataset.

